9.6 Data management

A Contract Research Organization (CRO) will be selected and assigned for EDC system development. The CRF will be part of the EDC system which allows documentation of all variables and covariates by all participating sites in a standardized way. Detailed information on data management, including procedures for data collection, retrieval and preparation are given in the Data Management Plan (DMP). DMP and information on the EDC system are available upon request (see Annex 1).

For information on quality control, refer to section 9.8.

9.7 Data analysis

9.7.1 Statistical considerations

Statistical analyses will be of explorative and descriptive nature. The study is not intended to test pre-defined statistical hypotheses.

All variables will be analyzed descriptively with appropriate statistical methods: categorical variables by frequency tables (absolute and relative frequencies) and continuous variables by summary statistics (i.e. mean, standard deviation, minimum, median, quartiles and maximum).

All analyses will be performed for the total study population (overall population) and separately for each participating country if patient numbers are sufficient and if required for local reasons. Whenever reasonable, data will be stratified by subgroups (e.g. age, sex, baseline characteristics).

All therapies documented in the following forms will be coded using the latest version of the World Health Organization Drug Global available at time of database lock.

• Prior and concomitant medication

Any diagnoses/diseases/event terms documented in the following forms will be coded using the latest Medical Dictionary for Regulatory Activities (MedDRA) version:

- Co-morbidities (medical history, concomitant diseases)
- Adverse events

Interim analysis will consist of demographic and baseline data of patients enrolled as well as available safety data. Further details will be given in the statistical analysis plan (SAP).

All statistical details including calculated variables and proposed format and content of tables will be detailed in the Statistical Analysis Plan (SAP). The SAP will be finalized before study database lock. The SAP is available upon request (see Annex 1).

9.7.2 Analysis of population characteristics

Demographic and other baseline characteristics, including clinical characteristics of the underlying disease (CKD, T2D), will be described by frequency tables or summary statistics. Other baseline characteristics will include UACR, eGFR, diabetes duration, serum potassium, systolic blood pressure, diastolic blood pressure, HbA1c and CKD stage. Some continuous variables will be categorized and presented in frequency tables in addition to summary statistics. Categories will be defined in the SAP.

The subjects medical history conditions will be displayed by a frequency table.

Subjects with prior and concomitant medication will be presented by frequency tables or summary statistics.

The standard of care for chronic kidney disease (including Beta Blocker, ACE-I or ARB, MRA, Any RAS Inhibitor) will be tabulated by patient frequencies.

Number of patients with minimum follow-up will be displayed by suitable categories. The mean and median length of follow-up together with the patient-years will be presented for the primary endpoint.

9.7.3 Analysis of primary endpoint(s)

Descriptive statistics will be used to analyze the following variables assessing the treatment patterns relating to finerenone:

- Reasons for introducing/discontinuing finerenone
- Planned and actual duration of treatment with finerenone
- Dose and frequency of finerenone treatment
- Actions taken after finerenone introduction (e.g continue treatment, addition of second therapy, interrupt treatment, discontinue treatment)
- Actions taken after finerenone interruption (e.g restart finerenone alone, introduce concomitant therapy, discontinue finerenone)
- Treatment pathways for secondary medications after introduction of finerenone,

Type, dose and duration of prior and concomitant therapies

Frequencies will be provided in summary tables along with graphical summaries such as sunburst plots.

Continuous variables will be summarized in tables with the appropriate measures (mean, median, SD, IQR).

More details will be provided in the SAP.

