Data sources	The investigator or a delegate collects historic data (demographic and clinical characteristics) from medical records, or else by interviewing the patient. Likewise, the investigator or a delegate collects treatment related data during visits that take place in routine practice.			

Study size	In total, 4000 patients are planned to be enrolled. The study is not aimed to confirm or reject pre-defined hypotheses. Therefore, the sample size was determined due to feasibility reasons.		
Data analysis	Statistical analyses will be of explorative and descriptive nature. The study is not intended to test pre-defined statistical hypotheses.		
	All variables will be analyzed descriptively with appropriate statistical methods: categorical variables by frequency tables (absolute and relative frequencies) and continuous variables by summary statistics (i.e. mean, standard deviation, minimum, median, quartiles and maximum).		
	All analyses will be performed for the total study population (overall population) and separately for each participating country if patient numbers are sufficient and if required for local reasons. Whenever reasonable, data will be stratified by subgroups (e.g. age, gender, baseline characteristics).		
	Interim analysis will consist of demographic and baseline data of patients enrolled as well as available safety data. Further details will be given in the statistical analysis plan (SAP).		
	All statistical details including calculated variables and proposed format and content of tables will be detailed in the Statistical Analysis Plan (SAP).		
Milestones	First Patient First Visit (FPFV) 15-May-2022		
	Last Patient First Visit (LPFV) 15-Oct-2024		
	Last Patient Last Visit (LPLV) 15-Nov-2025		
	Clean Database (CDB) 15-Feb-2026		
	Study Report 15-Aug-2026		

5. Amendments

None

6. Milestones

Table 1 presents planned milestones for the project. These milestones are based on a timely review and approval of the project. Administrative changes to milestones due to delays in study preparation and enrolment do not require amendments to the protocol. Revised study timelines and milestones which do not constitute a need for a formal protocol amendment are kept as stand-alone document (Annex 1) that is available upon request.

Table 1: Milestones

Milestone	Planned date
Start of data collection (FPFV)	15-May-2022
Annual safety report	2022-2025
Interim analysis> FPFV+1 year	15-May-2023
Interim analysis> FPFV+2 year	15-May-2024

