9.1 Study design

This international study is a prospective, non-interventional multicenter, single arm study of patients with a diagnosis of CKD associated with T2D who are newly prescribed finerenone under routine

21785 FINE-REAL; V 1.0; 09 February 2022; based on template version 15

Page 16 of 48

treatment conditions. It is planned to enroll 4000 patients with a diagnosis of CKD and T2D for whom the decision was taken by the treating physician to initiate treatment with finerenone. Patients will be recruited within a period of approximately 30 months and followed up until 30 days after permanent discontinuation of finerenone, or until death, withdrawal of consent, end of study, or loss-to-follow-up, whichever occurs first. In case of a temporary finerenone treatment pause of ≤ 6 months, patients should stay in the study and followed up as planned. Finerenone treatment pauses of > 6 months are considered as permanent treatment discontinuation and end of observation should be documented in such cases (please also refer to section 9.2.5). End of study will occur 12 months after last patient first visit, allowing that each patient can be followed up for a minimum of 12 months.

In the event that the Chinese Heath Authority requires this study to be a PAC, then free drugs-finerenone will be provided for Chinese patients as requested per local guidelines for such studies. All study drugs are from commercial supplies and relabeled according to the relevant requirements. All study drugs will be distributed by an authorized drug responsible person such as pharmacist or study nurse.

9.1.1 **Primary endpoint(s)**

The primary endpoint is to describe treatment pattern in patients with CKD and T2D treated with finerenone, based on:

- Clinical characteristics of patients with CKD and T2D
- Reasons for introducing finerenone
- Reasons for discontinuation of finerenone
- Planned and actual duration of treatment with finerenone
- Dosing of finerenone
- Use of secondary therapies (concomitant medication) in patients with CKD and T2D.

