9.2.5 Visits

The investigator or a delegate documents an initial visit, follow-up visits and the end of observation/final visit for each patient in the Case Report Form (CRF). Initial and follow-up visits occur during routine practice, the study protocol does not define exact referral dates for those visits.

The observation period for each patient will be at least 12 months or the whole treatment period with finerenone if patient permanently discontinues treatment prematurely. Please note that during temporary finerenone treatment pauses of ≤ 6 months, the patient should stay in the study. In the context of this study, treatment pauses > 6 months are considered as permanent treatment discontinuation leading to end of observation. For such cases, the date of the first visit after a treatment pause of > 6 months should be considered as date for end of observation.

Premature end of therapy does not automatically imply end of documentation: the patient should be followed up at least 30 days after receiving the last finerenone therapy.

Baseline or Initial visit

Once a patient is found eligible for inclusion, the investigator or designated staff will inform the patient about the study. Where applicable, this will include discussing the patient information sheet (PIS) and informed consent form (ICF) and asking the patient to read and – when agreeing to participate – sign the informed consent.

Baseline information (considered as data collected no more than 1 month prior to the 1st dose of finerenone) recorded with the status at initial visit before the first drug administration.

Follow-up visit(s)

It is assumed, that according to clinical practice, follow-up visits will happen approximately every 3 months during the 1st year of treatment and every 6 months thereafter.

21785 FINE-REAL; V 1.0; 09 February 2022; based on template version 15

Page 19 of 48

During that timeframe, each visit near this time points performed per routine clinical practice should be documented.

End of Observation/Final Visit

The final data collection (end of observation) is after 36 months or at the end of study (whatever is earlier).

At this final observation point, the patient's condition and a treatment assessment will be documented, including:

- Date of final data collection
- Date of last dose of finerenone
- Therapy status at end of observation

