9.5 Study size

Global study

4000 patients are planned to be enrolled.

The aim of the study is to describe treatment patterns and to obtain useful estimates with adequate precision for safety outcome endpoints. The study is not aimed to confirm or reject pre-defined hypotheses. Therefore, the sample size was determined due to feasibility reasons.

Treatment patterns will be analyzed by using descriptive statistics, such as frequencies for categorical variables and sample statistics for continuous variables, as described in section 9.7.3 Confidence intervals are not applicable.

For the secondary endpoints incidence proportions, cumulative incidences and incidence rates will be estimated and corresponding two-sided 95% confidence intervals will be provided, as described in section 9.7.4.

With a sample size of 4,000 patients, for potential incidence proportions of 1%, 5%, 10% and 50%, respectively, the following precisions can be expected:

# of patients	Incidence proportion (%)	95% CI of incidence proportion	Width (%) of 95% CI
4,000	1%	(0.7%, 1.4%)	0.7%
	5%	(4.3%,5.7%)	1.4%
	10%	(9.1%, 10.9%)	1.9%
	50%	(48.5%, 51.5%)	3.1%

The 50% incidence proportion maximizes the precision width, therefore, maximum width with 4,000 patients will not be greater than 3.1%.

Subset China

400 patients are planned to be enrolled from China. For potential incidence proportions of 1%, 5%, 10% and 50%, respectively, the following precisions can be expected:

# of patients	Incidence	95% CI of	Width (%) of
	proportion (%)	incidence	95% CI
		proportion	
400	1%	(0.0%, 2.0%)	2.0%
	5%	(2.9%, 7.1%)	4.3%
	10%	(7.1%, 12.9%)	5.9%
	50%	(45.1%, 54.9%)	9.8%

The 50% incidence proportion maximizes the precision width, therefore, maximum width with 400 patients will not be greater than 9.8%.

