9.7.5 Analysis of further endpoints

Reasons, frequency and duration of inpatient, outpatient and emergency visits will be summarized by descriptive statistics. For diabetic retinopathy, frequency tables describing the severity will be presented for each eye data permitting.

More details will be provided in the SAP.

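### Section 9.7.3 names only plain summaries for actual treatment duration, a primary-endpoint item that is right-censored for patients still on finerenone when observation ends

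*Protocol*

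**What the plan says.** Protocol section 9.7.3 lists "Planned and actual duration of treatment with finerenone" among the treatment-pattern variables of the primary endpoint (also in 9.1.1 and 9.3.1). It states the method for all continuous items: "Continuous variables will be summarized in tables with the appropriate measures (mean, median, SD, IQR". Section 9.7.1 prescribes the same kind of summary for every continuous variable.

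The follow-up rules are these:
- Section 9.1: "Patients will be recruited within a period of approximately 30 months and followed up until 30 days after permanent discontinuation of finerenone", or to an earlier terminating event such as death, withdrawal or end of study.
- Section 9.1: "End of study will occur 12 months after last patient first visit".
- Section 9.2.5: "The final data collection (end of observation) is after 36 months or at the end of study (whatever is earlier".

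On precision for treatment patterns, section 9.5 says "Confidence intervals are not applicable". For the secondary endpoints, by contrast, sections 9.5 and 9.7.4 plan 95% intervals and rates per 100 patient-years, and 9.7.4 adds Aalen-Johansen curves for hyperkalemia. Section 9.7.2 plans follow-up length and patient-years, and section 9.2.5 collects the date of last dose and the therapy status at the end of observation. Sections 9.7.1 and 9.7.3 leave further detail to the SAP.

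**The concern.** A patient who is still taking finerenone at close-out or at the 36-month cap has not completed a treatment duration; what is recorded is the time observed so far. Putting these values into a mean or median alongside completed durations gives a number that depends partly on how long patients stay on drug and partly on when they were enrolled. Section 9.7.3 names no way of separating the two, although the protocol already uses a suitable estimator for hyperkalemia.

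A study whose primary aim is to describe treatment patterns will be read for how long patients stay on treatment. A plain median of 20 months could be taken as the typical time to discontinuation when it is not. Section 9.7.1 also allows country analyses, and section 7 says that the study starts in each country after local approval. A country that starts late would have a shorter possible duration even with identical persistence, and with no interval around the figure.

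**Working it through.** **Plan's own figures.** The milestones in the Abstract and Table 1 begin with "First Patient First Visit (FPFV) 15-May-2022", followed by last patient first visit on 15-Oct-2024 and last patient last visit on 15-Nov-2025. That is 29 months of recruitment plus 13 months, 42 in total. Section 9.1 gives about 30 plus 12, also 42. Possible observation is therefore 12–13 months for the last patient and 36 for anyone enrolled in the first 42 − 36 = 6 months.

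The largest interval width in section 9.5 for N = 4000 reproduces: 2 × 1.96 × √(0.5 × 0.5 / 4000) = 3.1 percentage points. For N = 400 it is 9.8 points, as stated.

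**Assumptions (not in the protocol).** All-cause stopping occurs at a constant rate r per year. The only discontinuation figures given, 2.3% and 1.2% in section 7, concern hyperkalemia alone, so r is varied from 10% to 50%. Entry is uniform over 30 months, with close-out at month 42 and the 36-month cap.

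**Formulas** (m in months).
- Share still on drug at m: S(m) = (1 − r)^(m/12).
- Share whose possible observation exceeds m: G(m) = 1 for m < 12, and (42 − m)/30 for 12 ≤ m < 36.
- True median: 12 × ln 2 / (−ln(1 − r)).
- Plain median of observed duration: the m at which S(m) × G(m) = 0.5.
- Share on drug at end of observation: 0.2 × S(36) + (1/30) × ∫ S(c) dc from 12 to 36, where 0.2 = 6/30 is the share that reaches the cap.

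**Numbers put in.**
- r = 20%: true median 12 × 0.693/0.223 = 37.3. At m = 20.2, S = 0.687 and G = 21.8/30 = 0.727, product 0.499.
- r = 30%: true median 12 × 0.693/0.357 = 23.3. At m = 17.1, S = 0.602 and G = 24.9/30 = 0.830, product 0.499.
- r = 50%: true median 12.0. Every patient can be observed that long, so G = 1 and the plain median is also 12.0.

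| Assumed stopping per year | Still on drug at end | Plain median | True median | Persistence at 12 / 24 months |
|---|---|---|---|---|
| 10% | about 80% | 23.5 | 78.9 | 90% / 81% |
| 20% | about 62% | 20.2 | 37.3 | 80% / 64% |
| 30% | about 47% | 17.1 | 23.3 | 70% / 49% |
| 50% | about 24% | 12.0 | 12.0 | 50% / 25% |

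Using 29 + 13 months instead gives plain medians of 20.7 at 20% and 17.6 at 30%, so the choice hardly matters.

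**Effect of enrolment timing alone.** Persistence is held fixed and entry is made late-loaded (Beta(2,1)), uniform, or early-loaded (Beta(1,2)).
- r = 10%: plain median 19.0, 23.5 and 29.8 months.
- r = 30%: 15.3, 17.1 and 20.5 months.
- r = 50%: 12.0 in all three, although the plain mean still moves (12.1, 13.2 and 14.2).

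**What intervals would show.** With 80% persistence at 12 months and ignoring dropout, the 95% width is 2 × 1.96 × √(0.8 × 0.2 / 4000) = 2.5 points overall, and 7.8 points in a subset of 400, the planned size for China.

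**The case against.** The strongest reply is that this is SAP material. Section 9.7.3 speaks of appropriate measures, covers all continuous variables in one sentence, excludes no further estimator and defers detail. The protocol defines no persistence endpoint, and as a description of exposure observed within the study the plain summary is correct. Follow-up length and patient-years are reported alongside it, no hypothesis or decision rule depends on it, and country analyses are conditional on sufficient numbers. Much of this stands, and it lowers the severity. It does not remove the point: the only method named for this primary item, applied as written, cannot be read as time on treatment, and the exclusion of intervals in section 9.5 is a positive statement that an SAP adding them would contradict.

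A reader might infer more than the documents support:
- *Most patients will still be on drug.* The protocol gives no all-cause rate. Under the assumptions above this holds only below about 28% stopping per year (24% with early-loaded entry, 32% with late-loaded entry).
- *The result reflects enrolment dates instead of persistence.* It reflects both, and at 50% per year the median is undistorted whatever the accrual pattern. Close-out is not fully common either, since about 20% reach the 36-month cap first under uniform entry.
- *Kaplan-Meier would recover medians of 79 or 37 months.* Both lie beyond 36 months of observation, so the median would be reported as not reached. The gain there is in fixed-time persistence.
- *Healthcare use will be reported as raw counts.* Section 9.7.5 says only "Reasons, frequency and duration of inpatient, outpatient and emergency visits will be summarized by descriptive statistics". A rate per patient-year is a descriptive statistic, so this text is not an error.

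**Conclusion.** The point holds in limited form. Section 9.7.3 names only plain summaries for a primary-endpoint duration that is censored at close-out or at 36 months, and section 9.5 excludes intervals for it. If stopping is low to moderate, the plain median understates time to discontinuation by about 6 months at 30% per year (23.3 − 17.1) and about 17 at 20% (37.3 − 20.2), and it shifts with accrual. The median distortion vanishes at 50%. These sizes rest on assumed stopping rates, a constant hazard and uniform entry; that the recorded duration is a lower bound for patients still on drug rests on the protocol alone. This should be fixed, but it does not endanger the study, because the data needed for a proper estimate are already collected.

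**What to change.** 1. In section 9.7.3, label the mean, median, SD and IQR of actual duration as observed exposure.
2. Add time from first dose to permanent discontinuation, by Kaplan-Meier or by Aalen-Johansen with death as a competing event, censored at end of observation. Report persistence at fixed times, for example 6, 12 and 24 months, with 95% intervals, overall and in any country analysis that is run.
3. In section 9.5, replace the sentence that excludes confidence intervals so that these estimates carry them.

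As an optional addition, section 9.7.5 could state that visits are also given per patient-year.

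The cost is a wording change in the protocol, matching text in the SAP and a few tables. Date of last dose and therapy status at end of observation are already collected under section 9.2.5, so no new data are needed.

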9.7.4 Analysis of secondary endpoints

The analysis of the secondary endpoints will be of a descriptive nature. The use of endpoint refers to the secondary endpoints described in section 9.1.2.

The following metrics will be provided:

- Number and proportion of subjects with endpoint
- Number of occurrences of the endpoint
- Incidence rates of the endpoint per 100 patient-years

In addition, AEs will be classified by MedDRA PT using the latest version of MedDRA. A summary of AEs will be presented by primary System Organ Class (SOC) and Preferred Term (PT). Aggregate frequencies at the SOC level will be presented.

For hyperkalemia frequency tables will be provided and cumulative incidences will be provided in the form of Aalen-Johansen estimates and curves, given adequate data is available. More details will be provided in the SAP.

9.7.5 Analysis of further endpoints

Reasons, frequency and duration of inpatient, outpatient and emergency visits will be summarized by descriptive statistics. For diabetic retinopathy, frequency tables describing the severity will be presented for each eye data permitting.

More details will be provided in the SAP.

9.7.6 Analysis of safety data

Besides the analyses of the safety endpoints detailed in section 9.7.4, AEs/SAEs will be summarized based on the total study population (overall population).

The occurrence, duration, treatment, severity and outcome of AEs, SAEs, and ARs will be listed.

More details will be provided in the SAP.

9.8 Quality control

9.8.1 Data quality

Before study start at the sites, all investigators and other involved site personnel will be sufficiently trained on the background and objectives of the study and ethical as well as regulatory obligations. Investigators and site personnel will have the chance to discuss and develop a common

understanding of the OS protocol and the CRF. They will be trained on the importance to ensure that all relevant study data entered in the EDC should be retrievable from the patient's medical records.

A CRO will be selected and assigned for EDC system development, quality control, verification of the data collection, data analysis and data transfer to Bayer.

All observations will be recorded in a standardized CRF. After data entry, missing or implausible data will be queried, and the data will be validated. A check for multiple documented patients will be done.

Detailed information on checks for completeness, accuracy, plausibility and validity are given in the Data Management Plan (DMP).

Medical Review of the data will be performed according to the Medical Review Plan (MRP). The purpose of the Medical Review is to verify the data from a medical perspective for plausibility, consistency, and completeness and to identify potential issues that could affect the robustness of the collected study data or the progress of the study. Detailed information on the Medical review will be described in the MRP.

National and international data protection laws as well as regulations on observational studies will be followed. Electronic records used for capturing patient documentation (eCRF) will be validated according to FDA Code of Federal Regulations (CFR) Title 21, Part 11 [11]. 21 CFR 11 regulations describe the criteria to consider electronic records including e-signatures to be reliable and generally equivalent to paper records and handwritten signatures. They mandate access controls to ensure that only authorized individuals can use the system, additionally a computer-generated audit trail has to be in place to record the date and time of any actions to create, modify, or delete electronic records.

DMP, MRP and validation documentation are kept as stand-alone documents (Annex 1).

